Based on effects reported in previous literature using a similar experimental paradigm and participant populations^{9, 10}, we anticipate that 30 participants per group (N=90 total) will provide sufficient power to test the primary study hypotheses. Therefore, this study will recruit 90 healthy men and women aged 18-85. Subjects will be identified and recruited through multiple approaches. Local University and community postings will be used to identify and recruit the healthy control participants. Additionally, partnerships with collaborators within the Division of Physical Therapy, Emory School of Medicine and Emory Healthcare will be utilized in subject identification and recruitment. Initial contact may be made by [name] or one of his associates.

Informed Consent. The letter of informed consent will be used as a template to describe what is being asked of the participant, the risks and benefits associated with participation etc. to the participant. The consent form will be explained by a member of the research team. At this time the individual making contact will also be available to answer any specific questions that may arise. Informed consent will be conducted by either [name] or a research coordinator in private-either in the research lab or a single-occupant office.

In testing sessions performed at the Neural Plasticity Research Laboratory (NPRL), participants will undergo: 1) noninvasive targeting of cortical locations by stereotactic neuronavigation using transcranial magnetic stimulation (TMS), 2) TMS measures of cortical excitability and neurotransmitter signaling, and 3) a motor learning paradigm. The duration of the testing session will be less than 3 hours. Participants may also be asked to complete a single magnetic resonance imaging (MRI) session prior to testing in the NPRL. Overall, participants will complete up to two study visits.

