Inclusion Criteria. This study utilizes non-invasive brain stimulation, which is associated with minimal risk. To further minimize any risks associated with the stimulation, every subject will be informed of the potential risks of participation in the consent form and will complete a form that screens for any potential factors that could increase risk. The PI will use this information to determine eligibility. Inclusion criteria include (1) no history of movement impairment or neurodegenerative disease (2) right handedness (3) no contraindication to transcranial magnetic stimulation (TMS)¹¹ or magnetic resonance imaging (MRI).

[figure not shown]

Figure 1. Experimental Design. Visit 1 will consist of a MRI session to acquire a structural image that will allow us to identify the target site of stimulation. Visit 2 will consist of a motor learning paradigm, during which one of three TMS conditions will be applied: premotor cortex (PMC) stimulation, primary motor cortex (M1) stimulation, or sham stimulation.

Exclusion Criteria. Any participant will be excluded if they: 1) are outside the age range of 18-85, 2) have a history of head trauma or neurodegenerative disorder, or 3) report contraindications

to TMS. Participants over age 65 will be asked to complete the Montreal Cognitive Assessment, and participants with a score of 25 or lower (out of the “normal” range) will be excluded.

Experimental Design: Participants will complete up to three study visits: a MRI session and a TMS session (**Figure 1**). During the TMS session, participants will be randomly assigned to receive one of three types of stimulation during the motor learning paradigm: TMS over premotor cortex (N=20), TMS over primary motor cortex (M1, N=20), or sham TMS over premotor cortex (N=20). Groups will be gender- and age- matched. Motor performance and cortical excitability will be assessed before and after the motor learning paradigm.

MRI Acquisition

Enrolled participants may complete a MRI scan prior to the experiment to obtain a structural brain image that will be used for guided navigation during TMS protocols. T1-weighted images will be acquired at the Center for Systems Imaging at Emory University on a Siemens Prisma 3T scanner (TR = 7.4ms, TE = 3.7ms, flip angle $\theta = 6^\circ$, 1 mm isotropic resolution, scan time=3.2min). Data will be stored on Emory University’s secure network server.

TMS Procedures

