Guided navigation will be used throughout the session in real-time to ensure consistent spatial localization of TMS application. BrainSight software (Rogue Research Inc.) will be used to localize stimulation over the motor representation associated with the target muscle, which will be the first dorsal interosseous (FDI) muscle of the hand. Electromyography (EMG) will be used to measure TMS-motor evoked potentials (MEPs) of the FDI muscle during all testing conditions. The resting motor threshold (RMT) will be defined for each hemisphere as the stimulus intensity required to elicit a MEP response greater than $50\mu\text{V}$ in over 50% of trials.¹² During the motor learning paradigm, sham or real TMS pulses will be delivered over premotor cortex or M1 at a stimulation intensity of 80% RMT time-locked to the presentation of specific visual stimuli (described in further detail below). Before and after the motor task, participants will receive blocks of TMS at 120% RMT and between 30 and 80% of maximum stimulator output to create an input/output curve to evaluate cortical excitability.

Motor Sequence Learning Paradigm

A modified version of the serial reaction time task (SRTT)¹³ will be used to assess motor sequence learning in all study participants (**Figure 2**). During this task, the left hand will be placed on a button box so that the four fingers will press specified keys. Four colored squares will appear on the screen, and participants will be instructed to press the button that corresponds to a target square located beneath the four colored squares. The button presses will occur in a repeating pattern, and response time will be measured to indicate how well the pattern is learned. There will be blocks of random sequences at the beginning and end of the test blocks that will be used

[figure not shown]

Figure 2. Example trials of SRTT. Four boxes on the top of the screen correspond to four buttons on a button box. The target box on the bottom indicates which button to press. The colors change each trial so the participant cannot learn the sequence of colors.

to assess general task performance, and there will be five blocks in between that will be used to train the sequence. A follow-up block of the task will be performed 30 minutes following training to test short-term retention of skill.

Risks and Discomforts:

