A skill score (SS) will be calculated as the difference between performance on the random blocks minus the average performance on the patterned sequence in the test block to determine how well the patterned is learned. Percent change in SS will be used to index sequence-specific motor learning while controlling for general improvements in motor performance. One-way ANOVA will be used to test for differences in sequence-specific skill acquisition and sequence-specific skill retention between the groups that received different types of TMS stimulation. R statistical packages will be used for statistical analyses. Secondary statistical analyses will use a repeated measures ANOVA to examine differences in cortical excitability before and after motor training. Significance level will be set at $\alpha \leq 0.05$.

Compensation:

Participants will get \$20 for each completed study visit, to compensate them for their time and effort. If they do not finish the study, we will compensate them for the visits they have completed. They will get \$40 total if they complete two study visits.

Data Safety and Monitoring

To ensure safety and minimize risks to study subjects, the following data safety monitoring plan (DSMP) will be implemented in accordance with the Emory University IRB DSMP guidance document:

The primary risk for subjects participating in this study is the risk of seizure associated with transcranial magnetic stimulation (TMS). Although no seizures have been reported as a direct result of the type of stimulation in this study, to minimize any risk of seizure, we will not enroll individuals with a history of seizure. A TMS screening form (adapted from ¹¹) will be administered for each subject prior to beginning the study to identify potential factors that would place the subject at increased safety risk (e.g. epilepsy or epileptogenic medications).

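### The protocol promises both random assignment and gender- and age-matched groups, but names no allocation method that delivers both

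*Combined protocol and SAP*

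**What the plan says.** Allocation is covered by two sentences in the Experimental Design section. The first reads: "During the TMS session, participants will be randomly assigned to receive one of three types of stimulation during the motor learning paradigm". The second, which follows the list of arms, reads: "Groups will be gender- and age- matched". No tolerance, age bands or matching procedure is given. The document nowhere mentions stratification, blocking, minimisation, sequence generation, concealment or who makes the assignment.

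The Participants and Recruitment section says "this study will recruit 90 healthy men and women aged 18-85", and "we anticipate that 30 participants per group (N=90 total) will provide sufficient power to test the primary study hypotheses". The Experimental Design section instead gives 20 per arm, 60 in total. That conflict is a separate matter, so both sizes are carried through here.

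Under TMS Procedures, staff localise the FDI representation and determine the threshold: "The resting motor threshold (RMT) will be defined for each hemisphere as the stimulus intensity required to elicit a MEP response". The training intensity is set from that threshold, and an input/output curve is recorded before the task. The protocol does not say whether the arm is known during these steps.

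The Statistical Plan's primary analysis is: "One-way ANOVA will be used to test for differences in sequence-specific skill acquisition and sequence-specific skill retention between the groups". It names no age or gender term.

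**The concern.** Age could plausibly affect both response times and cortical excitability, and eligibility spans 67 years (85 − 18). The authors evidently want the arms comparable on age and gender. Plain randomisation at 20 or 30 per arm does not reliably give that, and the one-way ANOVA does nothing about it afterwards.

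A team that takes the matching sentence seriously, with no written method, has two courses. It can randomise plainly and often miss the promise. Or it can adjust later assignments by hand to keep the arms alike, which would weaken the randomised comparison. The trial's purpose is a causal statement about which cortical area is involved in learning, and that statement rests on how people enter the arms.

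Timing adds to this. Hotspot, threshold and baseline excitability all depend on the operator, and assignment takes place in the same session. The protocol should say that these are recorded before the arm is known.

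**Working it through.** There is no stated balance figure to reproduce. The check asks how often plain randomisation gives arms that one would not call matched, and whether a restricted random method does better.

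**Inputs from the document:** three arms of equal size; 20 per arm (Experimental Design) or 30 per arm (Participants and Recruitment); ages 18-85.

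**Assumptions, because the document gives no distribution:** 50% women; ages uniform on 18-85, with uniform on 18-50 as a narrower alternative.

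**Step 1. Spread of the difference between two arms.**

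- Age SD, uniform on 18-85: (85 − 18)/√12 = 19.34 years. The SD of the difference between two arm means is 19.34 × √(2/20) = 6.1 years at 20 per arm and 19.34 × √(2/30) = 5.0 years at 30.
- Age SD, uniform on 18-50: (50 − 18)/√12 = 9.24 years, giving 9.24 × √(2/20) = 2.9 years and 9.24 × √(2/30) = 2.4 years.
- Share of women: √(2 × 0.5 × 0.5/20) = 0.158 at 20 per arm and √(2 × 0.5 × 0.5/30) = 0.129 at 30.

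**Step 2. Largest gap among three arms under plain randomisation, by simulation.** A 20-point gap in the share of women means 4 people at 20 per arm (0.20 × 20) and 6 at 30 (0.20 × 30).

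| Largest between-arm gap | 20 per arm | 30 per arm |
|---|---|---|
| Share of women, 20 points or more | about 51% | about 33% |
| Mean age over 5 years, ages 18-85 | about 70% | about 58% |
| Mean age over 10 years, ages 18-85 | about 24% | about 11% |
| Mean age over 5 years, ages 18-50 | about 20% | about 9% |

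The age rows depend heavily on the assumed spread. An intermediate age SD of 15 gives about 54% for a gap over 5 years at 20 per arm. The gender row does not depend on the ages.

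**Step 3. Random methods that balance on both factors**, with ages uniform on 18-85 and 50% women.

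| Method | Per arm | Gender gap 20 points or more | Mean-age gap 10 years or more | Median mean-age gap |
|---|---|---|---|---|
| Plain randomisation | 20 | 0.51 | 0.24 | 6.9 years |
| Stratified blocks of 3, gender × 3 age bands | 20 | 0.000 | 0.000 | 2.9 years |
| Minimisation with a random element | 20 | 0.001 | 0.002 | 2.9 years |
| Plain randomisation | 30 | 0.32 | 0.11 | 5.6 years |
| Stratified blocks of 3, gender × 3 age bands | 30 | 0.000 | 0.000 | 2.2 years |
| Minimisation with a random element | 30 | 0.000 | 0.000 | 2.1 years |

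The 0.32 here and the 33% in Step 2 for gender at 30 per arm differ only by simulation error.

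Restricted randomisation therefore meets both sentences closely at either size, with no one choosing an arm.

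**The case against.** The strongest reply is that the two sentences do not conflict. Random assignment need not mean unrestricted assignment, and Step 3 shows that stratified blocks or minimisation satisfy both. That stands. A reader might infer that randomisation cannot give matched groups at this size, or that staff must steer assignments. Neither follows, and nothing in the protocol says that staff choose arms.

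A reader might also infer that the operator knows the arm while finding the hotspot and setting the threshold. The document does not say so. It places assignment somewhere in the TMS session, and the Participants and Recruitment section lists targeting, then excitability measures, then the learning task, which is equally compatible with late assignment.

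Nor do the documents support a claim that covariate adjustment would be useless. If assignments were steered only on recorded age and gender, adjusting for those variables could address it. Selection on unrecorded traits would be a different matter, but nothing in the text points to it.

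Chance imbalance under true randomisation is not bias and leaves the type I error of the ANOVA intact. The Step 2 percentages therefore show how often the matching promise would be missed, not how biased the result would be. The age figures also shrink considerably with a narrower age range, which is plausible because recruitment is partly through university postings.

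What the reply does not remove is the gap itself. The protocol makes a promise about balance and gives no mechanism for keeping it.

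**Conclusion.** The concern holds as an unspecified allocation method. Plain randomisation would miss gender balance by 20 points or more in about half of trials at 20 per arm and a third at 30, assuming 50% women. It would leave a mean-age gap over 5 years in between 20% and 70% of trials at 20 per arm, and between 9% and 58% at 30, depending on whether ages span 18-50 or 18-85. Discretionary matching is a risk that the text leaves open, not a practice that it describes. The change is worth making because a standard method delivers the intended balance at almost no cost and protects the causal comparison.

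**What to change.** Replace the matching sentence with text along these lines: *Assignment follows a computer-generated list, stratified by gender and age band (for example 18-44, 45-64 and 65-85), in randomly varying block sizes. The list is prepared and kept concealed by a team member who does not enrol or test participants. The arm is revealed only after the FDI hotspot, resting motor threshold and pre-task input/output curve have been recorded, immediately before the motor task.*

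Revealing the arm at that point means the coil need not be set up partway through the task. The opening random block is then run after the reveal, but it is a button-press response time and depends less on the operator than the TMS measurements do.

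In the Statistical Plan, add gender and age (or age band) to the primary model, so that the analysis matches the allocation. With gender and three age bands this uses 1 + 2 = 3 degrees of freedom. The residual falls from 60 − 3 = 57 to 54, or from 90 − 3 = 87 to 84.

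**Cost:** a list must be prepared, the session order is fixed, and a few degrees of freedom are used. Balance is approximate rather than exact, and unfinished blocks across the 2 × 3 = 6 strata can leave the arm totals slightly unequal. No visits, procedures or participants are added, and an existing team member can hold the list.

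### The skill score does not say which random block is its reference, and neither natural reading of its change removes general practice gain as the plan says it does

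*Combined protocol and SAP*

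**What the plan says.** The Statistical Plan defines the score as follows: "A skill score (SS) will be calculated as the difference between performance on the random blocks minus the average performance on the patterned sequence". The patterned performance is taken from a test block that is not identified further. The same section then gives the index to be analysed and its purpose: "Percent change in SS will be used to index sequence-specific motor learning while controlling for general improvements in motor performance". The three stimulation groups are compared by one-way ANOVA on acquisition and on retention.

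The section Motor Sequence Learning Paradigm gives the position of the random blocks: "There will be blocks of random sequences at the beginning and end of the test blocks that will be used". It goes on to their role and to the training that separates them: "to assess general task performance, and there will be five blocks in between that will be used to train the sequence". Performance is measured by response time. Retention has its own block: "A follow-up block of the task will be performed 30 minutes following training to test short-term retention of skill".

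Four things are left open:

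- which random block, or blocks, form the reference for each score;
- which two scores make up the percent change;
- how many random blocks there are at each end;
- whether the 30-minute block contains random trials.

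**The concern.** Aim 1 asks about sequence learning, so the index has to separate knowledge of the sequence from getting faster at the task in general. The random blocks are there for that purpose, but subtracting them helps only if they differ between the two scores being compared. A reference common to both drops out of the change.

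Real or sham pulses are delivered over premotor cortex or M1 during the task itself, so an effect of stimulation on general response speed is plausible. If the index lets general speed through, such an effect would be read as an effect on sequence learning. That is the distinction the trial is meant to draw.

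**Working it through.** The documents give no response times, standard deviations or expected practice gains, so there is no figure of the plan's own to reproduce. The algebra below needs no assumptions about size. The numbers after it are illustrative.

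**Notation.** R0 and R6 are mean response times in the start and end random blocks. P1 and P5 are mean response times in the first and fifth patterned blocks. First-to-last is taken as the change, because the plan names no time points.

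**Algebra**

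- Common reference R (both random blocks together, or the start block alone): (R - P5) - (R - P1) = P1 - P5. This is the raw speed-up on the pattern, for any shape of practice curve. In percent change, (P1 - P5)/(R - P1), the random blocks enter only through the denominator.
- Time-matched (start random with P1, end random with P5): (R6 - P5) - (R0 - P1) = (P1 - P5) - (R0 - R6). This subtracts practice over the whole span from R0 to R6, but the patterned blocks cover only the shorter span from P1 to P5.
- End-adjacent score, with no change taken: R6 - P5. Only the practice between two neighbouring blocks is left.

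**Illustration.** Assumed: one random block at each end, positions t = 0 (random), 1 to 5 (patterned) and 6 (random), a general gain of 80 ms from position 0 to 6, and no sequence knowledge at all. A correct index would give 0. Gain by position t is 80 × t/6 (linear) or 80 × (1 - e^(-t/τ))/(1 - e^(-6/τ)) (exponential, τ in blocks).

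| Practice curve | Gain at P1 | Gain at P5 | Common reference: P1 - P5 | Time-matched: (P1 - P5) - 80 | End-adjacent: gain at P5 - 80 |
|---|---|---|---|---|---|
| Linear | 13.3 | 66.7 | +53.3 | -26.7 | -13.3 |
| Exponential, τ = 1.5 | 39.7 | 78.6 | +38.9 | -41.1 | -1.4 |
| Exponential, τ = 3 | 26.2 | 75.0 | +48.8 | -31.2 | -5.0 |

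All entries are in ms.

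**Between arms.** If the gain is the same in every arm, each entry is the same in every arm and cancels in a comparison of absolute change. Suppose instead that one arm's general gain is 20 ms smaller. Every entry scales with the gain, so the spurious difference is the entry × 20/80:

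- common reference: 13.3, 9.7 and 12.2 ms, making the slower-improving arm look as if it learned less of the sequence;
- time-matched: 6.7, 10.3 and 7.8 ms, making the same arm look as if it learned more;
- end-adjacent: 3.3, 0.4 and 1.2 ms, in the same direction as time-matched.

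**Percent change.** Assume a linear 30 ms general gain, a 20 ms advantage for the pattern at P1 and no further sequence learning. With R0 = 500, R6 = 470, P1 = 475 and P5 = 455 ms:

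- both random blocks averaged (485): score 10 to 30, or +200%;
- start block alone: 25 to 45, or +80%;
- time-matched: 25 to 15, or -40%.

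The true sequence-specific change is zero in all three. With a 60 ms gain, R0 = 500, R6 = 440 and P1 = 470 ms. The averaged reference is 470 ms, the early score is 0 and percent change is undefined.

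**The case against.** The strongest reply is that the plan never says the random blocks are pooled. A reader might infer from the plural that one averaged reference is used throughout, so that the index certainly fails to correct for practice. The documents do not support that. The Abstract speaks of change in skill after training, Experimental Design has motor performance assessed before and after the learning paradigm, and the random blocks are said to assess general performance. Pairing each random block with its neighbouring patterned block fits all of this, and that change does subtract general gain. This part stands: pooling is one reading, and even the sign of the error depends on a choice the plan does not state. It does not rescue the claim of control, because the time-matched change misses zero by 27 to 41 ms in the same model.

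A reader might also take +39 to +53 ms as the bias in the treatment comparison, or infer an inflated false-positive rate for the ANOVA. Neither follows. An equal gain cancels between groups for absolute change. The documents give no variability and no arm difference in general gain from which an error rate could be worked out, and the planned test is of percent change across three groups.

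Finally, the end-adjacent score replaces a change with a level, still leaks a little, and relies on a block exposed to fatigue or interference. All true. However, no one has practised the pattern before training, so the end-of-training level is itself a measure of acquisition. Any inherent ease of the pattern should be similar in randomised arms.

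**Conclusion.** The concern holds in this form: the index is under-specified, and under neither natural reading does a change in the score deliver the control that the plan claims for it. A common reference leaves general practice in, and a time-matched one takes too much out. That much is algebra, given that general practice occurs and that some of it falls outside the interval from the first to the last patterned block.

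The sizes rest wholly on assumed values: an 80 ms gain, one random block at each end, and linear or exponential practice. For the group comparison, what matters is whether stimulation changes general speed. With an assumed 20 ms arm difference in gain, the spurious difference is about 7 to 13 ms for either change score and 0.4 to 3.3 ms for the end-adjacent score. For percent change, cancellation between arms is not assured even when the gain is equal, because the early score in the denominator may be near zero.

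This is a cheap improvement, not a demonstrated error in a fully specified analysis.

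**What to change.** In the Statistical Plan:

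- Define the acquisition score as mean response time in the end random block minus mean response time in the last, adjacent patterned block.
- Compare that score between the three groups in place of percent change in the skill score.
- Use the start random block only as a baseline-speed covariate, not as a reference for end-of-training performance. The one-way ANOVA then becomes an analysis of covariance with the same three-group test.
- State the retention reference: random trials within the 30-minute block if it contains them, otherwise the end random block. The latter does not remove any general change in speed over the 30 minutes.

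The cost is wording only, since all the acquisition blocks are already collected. The downside is that a single random block is a noisier reference than two and may carry fatigue or interference from the training just finished.

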Characterizing cortical contributions to motor sequence learning

Cortical contributions to motor sequence learning

[name], DPT, PhD. Division of Physical Therapy, Department of Rehabilitation Medicine, Emory School of Medicine

Protocol Version 1 9/20/2019

NCT04138953

Characterizing cortical contributions to motor sequence learning

Abstract:

The long-term objective initiated with this study is to determine which brain areas functionally contribute to learning a motor skill. Our primary hypothesis is that premotor cortex (PMC) is necessary to learn a new motor skill. Healthy adults (age 18-85) will be recruited to participate in this study at the Emory University Rehabilitation Hospital. Participants may undergo a MRI scan to acquire a structural image of their brain to target noninvasive stimulation, using transcranial magnetic stimulation (TMS) to one of two brain areas: PMC or primary motor cortex (M1). A third group of individuals will undergo a placebo stimulation protocol. For all three groups, stimulation will be used to create a transient 'virtual lesion' during motor skill training.

Temporarily disrupting the normal activity of these brain regions during training will allow us to determine which regions are causally involved in learning a new motor skill. The primary outcome measure will be the change in skill after training in each group. We anticipate the group receiving sham stimulation or stimulation to M1 will have greater increases in skill learning than the group receiving stimulation to PMC.

Introduction and Background:

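### The learning index is a percent change in a signed difference score, so it has no value at a zero reference, the wrong sign below zero and extreme values near zero

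*Combined protocol and SAP*

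**What the plan says.** The Statistical Plan defines SS as the "difference between performance on the random blocks minus the average performance on the patterned sequence in the test block". The Motor Sequence Learning Paradigm section makes response time the measure, so a positive SS means the pattern is performed faster than random trials. The learning index follows: "Percent change in SS will be used to index sequence-specific motor learning while controlling for general improvements in motor performance". It is compared across the three groups by one-way ANOVA, for acquisition and for retention. The Abstract makes this the main result: "The primary outcome measure will be the change in skill after training in each group".

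No formula for the percent change is given, no reference block is named, and nothing covers a reference at or below zero. On timing, the Experimental Design section says "Motor performance and cortical excitability will be assessed before and after the motor learning paradigm", without saying whether that includes patterned trials. The task description has "There will be blocks of random sequences at the beginning and end of the test blocks", used "to assess general task performance, and there will be five blocks in between that will be used to train the sequence". Retention has its own block: "A follow-up block of the task will be performed 30 minutes following training to test short-term retention of skill". Stimulation runs through training: "During the motor learning paradigm, sham or real TMS pulses will be delivered over premotor cortex or M1".

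**The concern.** A percent change is meaningful when its denominator is positive and well away from zero. SS is a difference between two response times, and nothing in the design keeps it positive. If the reference is taken before or early in learning, SS should be close to zero by construction, because the pattern is not yet known. The index would then divide by the quantity expected to be smallest.

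Two things are at stake. First, any participant with a zero or negative reference gets no score or a score of the wrong sign on the primary outcome, and the analyst would have to invent a rule after seeing the data. Second, if small references are common, a few participants dominate the ANOVA, and a real premotor (PMC) effect is likely to be missed.

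The exposure differs by outcome. It is greatest for acquisition with an early reference. For retention the natural reference is end-of-training SS, which should be well above zero in most participants.

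**Working it through.** **The rule itself (no assumptions about the data).** Percent change = 100 × (SS_after − SS_ref) / SS_ref. For the same 40 ms gain:
- reference 60 ms: 100 × 40/60 = +67%
- reference 2 ms: 100 × 40/2 = +2000%
- reference −5 ms: 100 × 40/(−5) = −800%
- reference 0 ms: undefined

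A worsening from −20 to −40 ms scores 100 × (−20)/(−20) = +100%. An absolute-value denominator would mend the sign but not the undefined or extreme values.

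**The plan's own figure.** Participants and Recruitment says 30 per group gives sufficient power, but states no effect size, SD or power, so this cannot be reproduced. For orientation, a three-group ANOVA at alpha 0.05 has 80% power at Cohen's f of about 0.33 with 30 per group, or 0.41 with the 20 per group given in Experimental Design.

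**Assumed inputs for power (none is in the documents).** SS has SD 30 ms before and after; correlation 0.3; mean gain 40 ms under sham and M1; PMC deficit 21.3 ms, so PMC gains 18.7 ms. The deficit was set so that end-of-training SS would have about 80% power with 30 per group.

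**Check on change in ms.** SD of change = 30 × √(2 × 0.7) = 35.5 ms. The mean of 40, 40 and 18.7 is 32.9. Variance of the group means = (7.1² + 7.1² + 14.2²)/3 = 100.8. Noncentrality = 90 × 100.8/35.5² = 7.2, which gives 65% power whatever the reference mean.

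**Simulated power, additive gain, 30 per group:**

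| Reference mean above zero | References at or below zero | Percent change | Change in ms |
|---|---|---|---|
| 0.33 SD | 37% | 2% | 65% |
| 1 SD | 16% | 2% | 65% |
| 2 SD | 2% | 5% | 65% |
| 3 SD | 0.1% | 23% | 65% |
| 5 SD | about 0 | 49% | 65% |
| 8 SD | about 0 | 57% | 65% |

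With 20 per group: 2% against 46% (0.33 SD), 17% against 46% (3 SD) and 39% against 46% (8 SD). At 0.33 to 2 SD the most extreme of 90 participants carries a median 61–63% of the total sum of squares of percent change, against 8% in ms. ANCOVA in ms reaches 83–84% with 30 per group.

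**Proportional gain, 30 per group, percent change against change in ms:**

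| Reliability of SS | 2 SD | 3 SD | 5 SD | 8 SD |
|---|---|---|---|---|
| 1.0 | 80 vs 61 | 81 vs 71 | 80 vs 77 | 80 vs 79 |
| 0.9 | 24 vs 57 | 55 vs 65 | 69 vs 70 | 70 vs 71 |
| 0.7 | 11 vs 50 | 34 vs 54 | 52 vs 57 | 56 vs 58 |

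**Type I error of percent change for acquisition (correlation 0.3):** 1.8% at 0.33 SD, 1.5% at 2 SD, 3.3% at 3 SD and 4.9% at 5 SD.

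**Retention.** With assumed end-of-training means of 80 ms (sham, M1) and 58.7 ms (PMC), the reference lies 80/30 = 2.7 SD or 58.7/30 = 2.0 SD above zero, so values at or below zero are rare. If all groups instead start from the same SS and PMC loses an extra 15 ms, power for absolute against percent change is 37% vs 27% at correlation 0.3 and 58% vs 43% at 0.6.

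**Alternative reading.** Dividing the change in SS by random-block response time (assumed 450 ms with SD 60, or 500 ms with SD 100) gives 61–64% power against 65–66% in ms, a loss of about 2 to 5 points.

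**The case against.** The strongest reply is that the size of the problem rests on inputs nobody can see. SS mean, SD, correlation and form of gain are all assumed, and the loss runs from about 63 points to none, with reversal when gain is proportional and free of measurement error. That stands. A reader might infer from the 2% figure that this trial has almost no power, or that percent change is always the worse index. The documents support neither, because they do not say where the reference SS lies.

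A reader might also infer that the ratio is redundant because the subtraction inside SS already removes general improvement. That holds only if each SS uses a random block from about the same time. If one pooled random value serves every SS, it cancels from the change and controls nothing. Subtraction also leaves any scaling with overall speed, so with ages 18–85 a relative index has a fair rationale.

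A further temptation is to drop change altogether and compare end-of-training SS. It does well under additive gain (about 80%), but under proportional gain its power is only about 29–44%. With reliability 0.9 it then loses to percent change at 3 to 8 SD. It also abandons the change in skill named in the Abstract, and a last training block is recorded under stimulation, so immediate disruption could be mistaken for poor learning.

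Finally, the authors may have meant SS relative to random-block response time. That would remove the defect, but the text does not say it.

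**Conclusion.** The point holds and should be corrected before analysis. The firm part is the rule: the index behind the primary outcome has no value at a zero reference, reverses sign below zero and is extreme near zero, and nothing elsewhere in the plan prevents this. That follows from the stated definitions alone.

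The power loss is conditional. Under additive gain it is severe when the reference mean is within about 2 SD of zero, still large at 3 SD and modest by 8 SD. With proportional gain and reliability 0.9 the two indices are equal by 5 to 8 SD. The exposure is mainly in acquisition with an early reference, and much less in retention. A reader might infer a risk of false positives for acquisition. The simulations do not show one; the risk is a missed effect.

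**What to change.** In the Statistical Plan, replace percent change with absolute change in SS (ms) for acquisition and retention, keep the one-way ANOVA, and report mean differences with 95% confidence intervals.

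- **Blocks.** Name the reference block, and pair each SS with the random block nearest in time. Say whether the 30-minute block contains random trials. If it has none and the closing random block serves both SS values, retention is only the change in patterned response time.
- **Acquisition.** If the before and after assessments in Experimental Design include patterned trials without stimulation, use those. Preferably analyse them by ANCOVA of the after SS on group, with the before SS as covariate. Do not use a training block recorded under stimulation as covariate.
- **Outcome.** Do not substitute an end-of-training level for change.
- **Relative index, if wanted.** Divide the change in SS by random-block response time, which is always positive, and write the formula out.

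The cost is mainly wording. Adding an unstimulated patterned block, if none is planned, would be a design change. Results would be in ms, and power would be somewhat lower if gain is truly proportional and measured without error. The change does not make up for a small sample: with 20 per group, change in ms has 46% power under the additive assumptions.
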